2.1.2 Secondary Objectives

2.2.2.1

To assess the highest grade of CTCAE version 5 radiation dermatitis during radiation treatment

2.2.2.2

To assess the time to occurrence of CTCAE version 5 grade 2 or higher acute radiation dermatitis.

2.2.2.3

To assess the time to healing if CTCAE version 5 grade 2 or higher acute radiation dermatitis develops.

2.2.2.4

To evaluate quality of life via acute and long-term symptoms and symptom scores utilizing the SkinDex16 scoring system.

2.2.2.5

To evaluate the threshold dose at which RD appears in either arm, utilizing skin dose tracking structures (V20 to V80 in 5 Gy increments reaching skin shell contours of "skin minus 3 millimeters" and "skin minus 5 millimeters")

2.2.2.6

To evaluate the threshold dose at which RD appears in either arm, using the same metrics as in 2.2.2.5, but with a new simulation scan in the last week of radiotherapy

2.2.2.7

To evaluate the effect of dermaprazole on inflammatory markers: CRP, TNFa, IL-1b, IL-6, by measuring values before, during, and after treatment. We expect this to give further evidence for the mechanism of action of dermaprazole.

Page 4 of 23

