5.6 Post-Treament Follow-Up

Patients will be followed for up to 60 months after completion of radiation or until death to assess intervention-related tolerance. See study calendar.

- 1. Month 1 visit (30 days after completion of all radiation therapy, +/- 14 days)
- 2. Month 3 visit (90 days after completion of all radiation therapy, +/- 28 days)
- 3. Long Term Follow-Up Visits: Month 6 (M6), Month 9 (M9), Month 12 (M12), Month 18 (M18), Month 24 (M24), Month 36 (M36), Month 48 (M48), and Month 60 (M60) (calculated from completion of all radiation therapy, +/- 28 days)

Assessments include:

- Focused skin exam
- Adverse event/toxicity evaluation, including CTCAE version 5 evaluation of radiation dermatitis with note of components (erythema, epilation, fibrosis, etc)
- SkinDex16 guestionnaire
- Photographic documentation of skin reaction with dermatologist's evaluation of CTCAE version 5 from this photography

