6 TREATMENT EVALUATION

6.1 Calendar of Study Assessments & Testing

		Head/Neck RT(Weekly) ^a								
	Baseline	Week 1	Week 2	Week 3	Week 4	Week 5	Week 6	Week 7	Week 8	Week 9 ^h
SCREENING										
Written Informed Consent	Х									
Inclusion/Exclusion Criteria	Х									
PHYSICAL										
Comprehensive History and Physical (ECOG only at Baseline)	Х									
Focused Skin Exam (Radiation Oncologist)	Х	Х	Х	Х	Х	Х	Х	Х		
Medical Photography ^d	Χ	X	Х	Х	Х	Х	Х	Х		
ASSESSMENTS										
CTCAE Version 5 Radiation Dermatitis (Radiation Oncologist)		Х	Х	Х	Х	Х	Х	Х		
CTCAE Version 5 Radiation Dermatitis (Blinded – Dermatologist)		Х	Х	Х	Х	Х	Х	Х		
Adverse Events/Toxicity		Х	Х	Х	Х	Х	Х	Х		
SkinDex16 Questionnaire	Χ	Х	Х	Х	Х	Х	Х	Х		
TREATMENT										
CT Simulation	Х							Χg		
XRT		Х	Х	Х	Х	Х	Х	Х		
Dermaprazole or Aquaphor ^c	Х	Х	Х	Х	Х	Х	Х	Х	Х	Х
Compliance Assessment	X ^f	X	Х	Х	Х	Х	Х	Х		Х
LAB DRAW										
Serum Pregnancy Test if Woman of Child-Bearing Potential	Х									
WBC, Hgb, ALT, AST, creatinine, calcium captured from clinical labse	Х	Х	Х	Х	Х	Х	Х	Х	Х	Х
Research Blood Draw to Central Lab: CRP, TNFa, IL-1b, IL-6	X							Xp		Х

- (a) Weekly assessments to be performed within +/- 3 days of the end of each week (defined by a period of 5 treatments).
- (b) In the last week of radiotherapy, may be different than week 7 $\,$
- (c) See Section 5.3 for detailed instructions regarding Dermaprazole and Aquaphor
- (d) Photos will be taken with a Canon EOS Rebel T7 DSLR Camera with 18-55mm Lens. Photos will be uploaded to a protected research folder directly from the camera and the dermatologist will have access to the folder. The photos will be de-identified and labeled with study case number.
- (e) WBC, Hgb, ALT, AST, creatinine and calcium data will be obtained from standard care clinical labs during treatment. If labs are not being drawn then they will not be obtained for the study.
- (f) Compliance assessment may be performed by telephone by research staff from Baseline to start of XRT
- (g) CT Simulation to be done anytime during the last 7 days of radiation treatment
- (h) Week 9 is defined as 2 weeks post last radiation treatment ± 5 day

Page 12 of 23

	Post-Treatment Assessment		Long Term Follow-Up Up to 60 months post-tx		
	Month 1 30 days post-tx ⁱ	Month 3 90 days post- ^{txj}	Every 3 Months M6, M9, M12j	Every year M24, M36, M48, ^{M60j}	
PHYSICAL					
Focused Skin Exam (Radiation Oncologist)	X	X	X	X	
Medical Photography	X	X	X	X	
ASSESSMENTS					

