8 STATISTICAL CONSIDERATIONS

8.1. Study Design/Endpoints

This portion of the study is designed to evaluate toxicity profile and preliminary efficacy of prophylactic Dermaprazole cream for radiation dermatitis in head and neck cancer patients receiving chemoradiation.

The first primary outcome is rates of clinically significant radiation dermatitis as defined as NCI CTCAE version 5 grade 2 or higher. Although not expected, if half our expected enrollment in the Dermaprazole group, 50% or more of patients experience moderate intervention-related toxicity, this treatment regimen will not be considered safe. The trial will be monitored for SAEs and stopped early for safety if two treatment-related grade 3 SAEs are reported or if one treatment-related grade 4-5 SAE is reported at any point of the trial for the Dermaprazole group.

Another primary endpoint will be feasibility, which is defined as the consideration of whether the protocol implementation will be successful in terms of accrual within the expected timeframe, as well as whether patients would comply with the study protocol and necessary data collection is logistically feasible in the clinical setting. To evaluate feasibility, we will measure:

Page 14 of 23

- Accrual rate and summary of causes for non-enrollment
- Percentage of patients compliant with therapy, defined as receiving at least 60Gy to the head and neck while using prophylactic Dermaprazole as directed
- Compliance rate and rate of completion of SkinDex16 forms

All endpoints will be evaluated when the last patient completes their 3 Month follow-up visit, although patients will continue with additional regular follow-up visits as described in the protocol schedule. Since by that point a patient would have completed all treatments, the data would provide accurate estimate of compliance and acute toxicity.

For the study to be considered feasible, all of the following must be true:

- No more than 5 patients fail to complete the treatment regimen due to study drug toxicity
- No more than 15 patients fail to comply to prophylactic Dermaprazole cream application of at least 80%
- Enrollment takes no longer than 24 months, and
- Proportions of analyzable questionnaires at baseline, while on-treatment, and offtreatment during follow-up, and within questionnaires completion rates are no worse than 80%, 80%, and 60% respectively.

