8.3 Analysis of Primary and Secondary Endpoints

Descriptive and summary statistics will be computed for demographic and clinical data of all subjects enrolled in the study to describe the study sample.

Toxicity will be reported as the frequency of each adverse event according to the CTCAE version 5.0 as well as the grade of each recorded adverse event (38). Generally, adverse events in this system are graded from 1 to 5, with 1 corresponding to either mild or asymptomatic clinical manifestations of toxicity and 5 corresponding to death related to the

Page 15 of 23

adverse event (see Appendix 2). Clinically relevant toxicity will be defined as grade 2 or higher, while severe toxicity will be defined as grade 3 or higher. Acute toxicity will be defined as adverse events that occur during or within 90 days after completing radiation therapy. We will consider this intervention safe if there is a grade 1 toxicity rate of <50%, a grade 2 or higher toxicity rate of <10% and no grade 3 or higher events.

Percentages of patients enrolled per month will be recorded. If the enrollment time exceeds 24 months, the study will be considered not feasible as written. Percentage of patients not enrolled will be summarized by cause.

Quality of life will be measured with the use of SkinDex16 questionnaires filled out by the patient at baseline, throughout treatment, at the completion of radiation treatment, and at each follow up visit subsequently. We will also consider the compliance to questionnaire completion and within questionnaires completion rates. This will be reported as the average proportion of questions within each form completed properly, without errors. As long as the rates are not below the minimum threshold defined above, the study will be considered feasible.

All analyses outside of the primary endpoint will be considered exploratory in nature. Chi square and t-test will be used to evaluate differences in categorical and numerical values between arms. Subgroup analyses for BMI, total dose, and comorbidity will be conducted. We will also evaluate the incidence of RD for specific radiation skin dose stratification by reviewing the V20 to V80 in 5 Gy increments reaching a skin shell representing the thickness between the skin and the "skin minus 3 millimeters" and the "skin minus 5 millimeters." This will be done on both the original dosimetry as well as a recalculated plan from the resimulation scan.

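### SkinDex16 is collected up to ten times per patient by the Month 3 analysis, but section 8.3 names only a between-arm t-test and does not say how the repeated, partly missing scores become one answer

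*Combined protocol and SAP*

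**What the plan says.** Section 2.1.2 (item 2.2.2.4) sets the objective: "To evaluate quality of life via acute and long-term symptoms and symptom scores utilizing the SkinDex16 scoring system".

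Section 8.3 describes collection as "SkinDex16 questionnaires filled out by the patient at baseline, throughout treatment, at the completion of radiation treatment, and at each follow up visit subsequently". The calendar in section 6.1 marks the form at Baseline and Weeks 1 to 7 ("Weekly assessments to be performed within +/- 3 days of the end of each week"), with none at Weeks 8 and 9, and again at each follow-up visit. Section 5.6 places the first two of these at "Month 1 visit (30 days after completion of all radiation therapy, +/- 14 days") and "Month 3 visit (90 days after completion of all radiation therapy, +/- 28 days"). Section 8.1 fixes the analysis time: "All endpoints will be evaluated when the last patient completes their 3 Month follow-up visit".

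The method is one general sentence in section 8.3: "Chi square and t-test will be used to evaluate differences in categorical and numerical values between arms". The sentence just before it classes everything outside the primary endpoint as exploratory. Section 8.3 later makes all tests two-sided.

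On missing forms, section 8.1 gives feasibility floors for analysable questionnaires at baseline, on treatment and in follow-up, "and within questionnaires completion rates are no worse than 80%, 80%, and 60% respectively". Section 8.4 limits the analysis to patients who received at least 60 Gy and attended the 30-day follow-up. Neither section says how a missing form is handled.

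**The concern.** A two-sample t-test takes one number per patient. SkinDex16 supplies up to ten, and the plan does not say which number, or which summary of them, enters the test. Three things are at stake.

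- **No single answer.** An analyst could test every visit, choose one visit, average the scores or take a change from baseline. All of these fit the sentence, and they can disagree. If the choice follows sight of the data, the multiplicity is hidden rather than removed.
- **Sensitivity.** With 30 and 15 patients, a test at one visit detects only a very large difference. Correlation between visits and with baseline is information already collected, and a plain t-test at one visit does not use it.
- **Missing forms.** The feasibility floors tolerate losing 20% of forms on treatment and 40% in follow-up. If patients with worse skin return fewer forms, a comparison of returned forms is biased, and the plan is silent on this.

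**Working it through.** **Inputs from the documents.** Arms of 30 and 15 (section 8.2). Two-sided tests (section 8.3). Alpha 0.05 and 80% power are stated for the primary sample size (section 8.2) and borrowed here. Form counts come from sections 5.6 and 6.1, and tolerated completion of 80%/80%/60% from section 8.1.

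**Assumptions.** The documents give no SD, target difference or between-visit correlation for SkinDex16. Differences are therefore in SD units, and the correlation ρ is assumed equal between all visits (compound symmetry) and varied.

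**The plan's own figure.** No figure is given for SkinDex16. The primary sample size does reproduce: 65% versus 20%, two-sided 0.05, 80% power, 2:1, no continuity correction gives 13 + 26 = 39. This bears on the primary endpoint only.

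**Form count.** 1 baseline + 7 weekly + Month 1 + Month 3 = 10, of which 9 are post-baseline. The form at completion of radiation is taken to be Week 7. A shorter course gives fewer.

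**False positives if each post-baseline visit were tested at 0.05.** If independent: 1 − 0.95⁹ = 37%. With correlated visits, simulation of 20,000 null trials at 30 versus 15 with complete data gives:

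| ρ | 0.3 | 0.5 | 0.6 | 0.7 | 0.8 | 0.9 |
|---|---|---|---|---|---|---|
| At least one p<0.05 | 33% | 27% | 24% | 21% | 17% | 12% |

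A separate recomputation gave 25% at ρ = 0.6. With 20% of weekly forms and 40% of follow-up forms missing at random, ρ = 0.6 gives about 29%.

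**Sensitivity of one t-test at one visit (noncentral t).**

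| Patients with forms | Detectable at 80% power | Power for 0.5 SD |
|---|---|---|
| 30 v 15 (complete) | 0.91 SD | 34% |
| 24 v 12 (80%) | 1.02 SD | 28% |
| 18 v 9 (60%) | 1.19 SD | 22% |

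**Sensitivity of a Week 1-7 summary (30 v 15, complete data, same effect every week).** Multiply 0.906 SD by the square root of the relevant variance:

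- Mean of seven scores: variance (1 + 6ρ)/7 = 0.571 at ρ = 0.5 and 0.657 at ρ = 0.6. Detectable: 0.69 and 0.73 SD.
- Change of that mean from baseline: variance (1 + 6ρ)/7 + 1 − 2ρ = 0.571 and 0.457. Detectable: 0.69 and 0.61 SD.
- Mean adjusted for baseline: variance (1 + 6ρ)/7 − ρ² = 0.321 and 0.297. Detectable: 0.51 and 0.49 SD.

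**Effect confined to Weeks 4-7 (illustration).** The seven-week mean carries 4/7 of the effect, so the adjusted contrast needs 0.514 × 7/4 = 0.90 SD or 0.494 × 7/4 = 0.86 SD in those weeks.

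**The case against.** The strongest reply is that the plan does not prescribe visit-by-visit testing. A reader might infer nine separate t-tests on whichever forms came back, but section 8.3 mentions neither visits nor returned forms in this connection. For the laboratory markers it does specify each of the three draws, and no such wording is attached to SkinDex16. A t-test on each patient's on-treatment mean, or on its change from baseline, fits the sentence equally well. This stands: the defect is silence, and the 24-25% is conditional on one reading and on an assumed correlation.

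Second, this is a pilot, section 8.3 calls these analyses exploratory, and it puts the emphasis on safety and tolerability. The plan does not undertake to control familywise error for SkinDex16. This also stands, and it limits the harm of a chance finding. It does not help sensitivity or settle which comparison answers 2.2.2.4.

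Third, setting 0.91 SD against 0.5 SD flatters the remedy, because it compares one unadjusted visit with an adjusted seven-week average. The fair comparator is the best t-test the sentence allows, 0.61-0.73 SD. The adjusted contrast is still more sensitive, by a smaller margin, and much of its advantage over one visit is lost if the effect occurs only in later weeks.

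Fourth, the 80%/80%/60% figures are feasibility floors, not forecasts. Requiring 30-day follow-up should reduce missing Month 1 forms. Fair; the missing-data figures show what the plan would tolerate, not what will happen.

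**Conclusion.** The point holds as a gap in the analysis plan with a concrete better method available. SkinDex16 is a named objective measured at up to nine post-baseline visits before the analysis. The only method named uses one number per patient, and that number is not defined.

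Under the t-test readings the text allows, the detectable difference at 80% power runs from 0.61 to 0.91 SD with complete data. One baseline-adjusted on-treatment contrast detects about 0.5 SD with a single 5% test. The summary-based figures assume correlation 0.5-0.6, compound symmetry, complete data and an equal effect every week; the gain is smaller if forms are missing or the effect comes late. The false-positive range of 12-37% applies only if visits are tested separately with complete data.

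Two stronger conclusions are not supported. A reader might take 24% as the error rate of this plan; the documents give neither the per-visit rule nor the correlation it needs. A reader might also expect a mixed model to cure missing-form bias. It addresses missingness explained by observed scores, not forms skipped because of that week's unseen skin condition.

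The primary endpoint is not affected.

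**What to change.** In section 8.3, add an analysis for objective 2.2.2.4:

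- One mixed model for repeated measures with arm, visit, arm-by-visit and baseline score, using all returned forms. State a covariance structure suited to 45 patients, and how a missing baseline form is handled.
- One named contrast as the answer: the mean arm difference over the on-treatment weeks, with its 95% confidence interval. Say how courses shorter than seven weeks enter that mean.
- Visit-specific differences, including Month 1, Month 3 and later follow-up, reported with 95% confidence intervals as description.
- A statement that the model assumes missingness is explained by observed scores, so some bias can remain if forms are skipped because of that week's skin condition.

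The cost is a few sentences and slightly more analysis work, with no new data or visits. The drawback is that averaging over the on-treatment weeks dilutes an effect limited to a few of them; the visit-specific intervals would show such a pattern.

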5.1 Baseline and Screening Evaluations

- Informed consent
- Review of inclusion/exclusion criteria
- Comprehensive History and Physical Exam (within 12 weeks of registration)
- ECOG Performance Status
- Pregnancy test (for women of child-bearing potential)
- SkinDex16 questionnaire
- Photographic documentation of skin at baseline
- WBC, Hgb, ALT, AST, creatinine and calcium taken from standard care clinical labs drawn closest to consent
- Research Blood Draw to Central Labs: CRP, TNFa, IL-1b, IL-6

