5.5 Assessments & Labs During Treatment

Weekly on-treatment assessments are as follows:

- Focused skin exam
- Adverse event/toxicity evaluation, including CTCAE version 5 evaluation of radiation dermatitis with note of components (erythema, epilation, fibrosis, etc)
- SkinDex16 questionnaire
- Photographic documentation of skin reaction with dermatologist's evaluation of CTCAE version 5 from this photography (photography may be discontinued if dermatitis radiation has resolved, or does not occur, at the discretion of the treating investigator or Principal Investigator)
- Compliance diary
- WBC, Hgb, ALT, AST, creatinine and calcium taken from standard care clinical labs
- Research Blood Draw to Central Lab: CRP, TNFa, IL-1b, IL-6 (in the last week of radiation and at 2 weeks after end of radiation)

Page 10 of 23

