8.2 Sample Size/Accrual Rate

Participants will continue to be enrolled and monitored for toxicity per the above criteria until 30 patients in arm 1 and 15 patients in arm 2 have completed the course of head and neck radiation as evaluable patients. Patients will be randomized by computer in a 2:1 fashion. Per our current database, the clinic is treating approximately 60 eligible patients per year. As such, accrual should take no longer than 12 months but will be allowed to extend to up to 24 months without closing the study.

Initial sample size for this pilot study was estimated as if this study was conducted as a phase II study. Sample size calculation was determined using significance/alpha (α) of 0.05, to at least detect a difference in incidence of 45% and power (β) of 80%. In general, rates of clinically bothersome grade II dermatitis in the literature appear to be approximately 65%. Based on our preclinical study with animal and human skin models, we expect 20% of the Dermaprazole arm to have CTCAE grade II or higher RD. Given these values, we calculated our final sample size to be approximately 39 and we aim to enroll 45 subjects.

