We will also evaluate any statistically significant differences in both the absolute numbers and relative changes of the lab values: CRP, TNFa, IL-1b, IL-6 at each of the 3 time points in which they are drawn for each arm.

All statistical tests will be two-sided. We will report comparative data in good faith and emphasize that the primary intention of this study is to understand the safety and tolerability profile of Dermaprazole.

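### The inflammatory-marker comparisons in 8.3 make poor use of the scheduled baseline draw; log-scale ANCOVA would be more sensitive for a change of wording only

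*Combined protocol and SAP*

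**What the plan says.** Secondary objective 2.2.2.7 in section 2.1.2 reads "To evaluate the effect of dermaprazole on inflammatory markers: CRP, TNFa, IL-1b, IL-6, by measuring values before, during, and after treatment", and adds "We expect this to give further evidence for the mechanism of action of dermaprazole".

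There are three draws. Section 5.1 lists the first among the baseline and screening evaluations: "Research Blood Draw to Central Labs: CRP, TNFa, IL-1b, IL-6". Section 5.5 places the other two "in the last week of radiation and at 2 weeks after end of radiation". The study calendar agrees, with the last draw at Week 9, defined as two weeks after the final radiation treatment.

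On analysis, section 8.3 says that significant differences will be sought in "absolute numbers and relative changes of the lab values: CRP, TNFa, IL-1b, IL-6 at each of the 3 time points", and the sentence closes with a reference to each arm. It names no test. The method comes from a general sentence earlier in 8.3: "Chi square and t-test will be used to evaluate differences in categorical and numerical values between arms". The sentence before that one sets the status: "All analyses outside of the primary endpoint will be considered exploratory in nature". All tests are two-sided.

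The plan specifies no covariate, transformation or rank test for the markers. It gives no reference point for relative change and no rule for values below an assay limit. It does not say whether the reference to each arm means a comparison between arms or within each arm over time.

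**The concern.** The baseline sample is scheduled for every patient, yet neither planned scale uses it well.

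- The absolute comparison at follow-up ignores baseline, so any chance imbalance between 30 and 15 patients passes straight into the result.
- Relative change divides each follow-up value by a single baseline reading. Measurement noise enters through the divisor, and patients with low baselines dominate the mean.
- At the first draw there is nothing useful to test. Relative change has no content there, and a difference in absolute values between randomised arms can only be chance.

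Inflammatory markers are often right-skewed. If these are, t-tests on the raw scale with 15 controls lose further sensitivity. At stake is whether the marker objective, the one the plan ties to mechanism, can show an effect of the cream that is really there.

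**Working it through.** **The plan's own figure.** The documents give no sample size, power, SD or correlation for the markers. The only sample-size figure is for dermatitis, 65% v 20%, with "significance/alpha (α) of 0.05", 80% power and 2:1 allocation. With pooled proportion (0.65 + 2×0.20)/3 = 0.35, the control arm needs

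[1.960·√(1.5×0.35×0.65) + 0.842·√(0.65×0.35 + 0.20×0.80/2)]² / 0.45² = (1.145 + 0.467)² / 0.2025 = 12.8, so 13.

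That gives 13 + 26 = 39, as section 8.2 states. The markers play no part in it. Below I take the 30 and 15 evaluable patients of 8.2.

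**Counting the comparisons.** Read literally, 4 markers × 2 scales × 3 draws = 24. Four of these are relative change at baseline, which is zero for everyone. Four are absolute values at baseline, where randomisation already makes the null true. That leaves 24 − 4 − 4 = 16. One baseline-adjusted analysis per marker and post-baseline draw would be 4 × 2 = 8.

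**Chance imbalance.** The between-arm difference in baseline means has SD √(1/30 + 1/15) = 0.316 marker SDs.

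**Detectable difference on a normal scale** (for example after logs), 80% power, two-sided 0.05. For a t-test on follow-up values it is (1.960 + 0.842) × 0.316 = 0.886 SD. A change score multiplies this by √(2(1−ρ)) and ANCOVA by √(1−ρ²), where ρ is the baseline to follow-up correlation.

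| ρ | follow-up only | change score | ANCOVA |
|---|---|---|---|
| 0.3 | 0.886 | 1.048 | 0.845 |
| 0.5 | 0.886 | 0.886 | 0.767 |
| 0.7 | 0.886 | 0.686 | 0.633 |

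**Simulated power on skewed data.** 30 v 15, log-normal marker, Dermaprazole halves the marker, two-sided 0.05. The distribution, log SD, ρ and effect are all assumptions. There were 10,000 trials per setting (8,000 for log SD 0.7), and repeat runs differ by a point or two.

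| log SD | ρ | raw t | percent-change t | log ANCOVA |
|---|---|---|---|---|
| 0.5 | 0.3 | 98% | 93% | 99% |
| 0.7 | 0.5 | 82% | 82% | 94% |
| 0.8 | 0.5 | 69% | 70% | 87% |
| 1.0 | 0.3 | 49% | 37% | 61% |
| 1.0 | 0.5 | 49% | 49% | 68% |
| 1.0 | 0.7 | 49% | 73% | 84% |
| 1.2 | 0.5 | 34% | 34% | 53% |

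Log ANCOVA was at least as powerful as both planned tests in every setting tried. With no effect, the raw t-test rejected in 3.4% to 4.7% of trials and the percent-change t-test in 3.5% to 5.1%. The loss is therefore in sensitivity and not in validity.

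**The case against.** The strongest reply is that little hangs on these tests. They are declared exploratory, 8.3 states that the main intention is to understand safety and tolerability, and no success criterion, stopping rule or sample size depends on the markers. That stands, and it keeps the point minor.

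Second, the reading is partly inferred. The marker sentence names no test, and its closing reference to each arm could mean within-arm comparison over time. That also stands, and it is a reason to clarify the text. Change within an arm cannot separate the cream from chemoradiation, so it would not answer objective 2.2.2.7. Likewise, relative change at baseline is probably loose wording that nobody would act on.

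Third, the size of the loss rests on assumptions. Log-normal data suit log ANCOVA exactly, and the effect is a halving. With a 20% reduction at log SD 1.0, all three methods have power of only about 9% to 16%. This is fair, but the direction does not reverse in any setting tried.

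A reader might go further and infer three things that the documents do not support.

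- **A false-positive rate of 64%.** That is 1 − 0.95²⁰ for 20 independent tests: four markers, each with three absolute values and two relative changes. The tests share data. Under assumed correlations the chance of at least one false positive is about 43% to 51%, and familywise error is not the governing standard for a declared exploratory analysis.
- **Patients dropping out because baseline is undetectable.** The documents give no assay limits or expected rate of such values, so this is only a possibility to provide for.
- **A need to name one lead marker.** The objectives rank none, and choosing one is a matter of preference.

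**Conclusion.** The concern holds as a minor efficiency point. Without any assumption about the data, the plan specifies no baseline adjustment for a baseline it schedules, and its wording includes comparisons at the first draw that cannot inform on treatment. How much sensitivity is lost depends on quantities that the documents do not give. For a halved marker, the gain of log ANCOVA over the better of the two planned tests is about 11 to 19 percentage points at log SD 1.0 (61 − 49 = 12, 68 − 49 = 19, 84 − 73 = 11). It is about 12 points at log SD 0.7 and ρ 0.5 (94 − 82), and small at log SD 0.5, where all methods exceed 93%. The planned tests keep their error rate near or below 5%. The primary result and the sample size are unaffected.

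**What to change.** In section 8.3, replace the marker sentence with text to this effect. Each of the four markers is compared between arms at the last-week draw and at the draw two weeks after radiation, by ANCOVA on the log scale with log baseline as covariate. The result is reported as a ratio of geometric means with a 95% CI. Baseline values are summarised by arm without a between-arm test. If any values fall below the assay limit, a rank-based analysis is added as a check. The results remain exploratory.

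This settles the between-arm or within-arm question and cuts the comparisons from a literal 24 to 8. It costs a change of wording and a little analysis work, and needs no extra patients, visits or samples, because the three draws are already scheduled. The wording should be fixed before marker results are compared by arm, so that the choice of model is not driven by the data.
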